10.2.2 Demographics

The following demographic information will have been collected at the Screening Visit of Cingal 16-02 trial: Age, Gender, Race and Ethnicity. The demographic data for Cingal 16-02 will be used for Cingal 17-02.

10.2.3 Physical Exam (PE)

The Physical Exam performed at the screening of Cingal 16-02 will be utilized for Cingal 17-02. The PE will include an assessment of general appearance, chest and lungs, heart, abdomen, skin, musculoskeletal system, neurologic systems and other (as applicable). This PE will include an assessment of height and weight for calculation of a BMI.

10.2.4 Vital Signs

Vital signs (blood pressure, pulse, temperature) at the screening of Cingal 16-02 will be utilized for Cingal 17-02.

10.2.5 Pregnancy Test

For females of childbearing potential, a urine or blood pregnancy test at the screening of Cingal 16-02 will be utilized for Cingal 17-02. Women who can confirm that they are surgically sterile or have been postmenopausal for at least 1 year prior to signing the ICF did need not undergo a pregnancy test in Cingal 16-02.

10.2.6 Chemistry/Hematology/Urinalysis

For all subjects, the blood tests at the screening of Cingal 16-02 will be utilized for Cingal 17-02. A routine and microscopic analysis of the urine at the screening of Cingal 16-02 will be utilized for Cingal 17-02.

Table 1 Laboratory Analytes		
Hematology	Clinical Chemistry	
Hematocrit	Sodium	AST/SGOT
Hemoglobin	Potassium	ALT/SGPT
RBC count	Chloride	Alkaline Phosphatase
WBC count	Glucose	Total protein
Differential WBC count	Urea nitrogen	Albumin
Platelet count	Creatinine	
HbA1c (for diabetics only)	Total bilirubin	
	Triglycerides	
	Calcium	

10.2.7 Knee X-rays/Assessment of Kellgren-Lawrence Score

Subjects will have completed screening within the Cingal 16-02 trial to have the following X-rays of both knees collected at the Screening Visit. The results of the X-rays of both knees in Cingal 16-02 will be utilized for Cingal 17-02:

- Long Limb Standing Anterior Posterior (AP) view
- Fixed Flexion Posterior Anterior (PA) view

These screening images will have been transferred to, as well as handled by, the Central Imaging Core lab according to their Standard Operating Procedures (SOPs). An independent radiologist from the Central Imaging Core lab will have evaluated the Screening plain films of both knees for osteoarthritic changes using the K-L scoring system (Appendix 4) and excluded subjects with K-L severity grade of IV in the index knee or K-L severity grade III or IV in the contralateral knee. Additionally, varus/ valgus alignment will have been assessed in both knees and subjects with greater than 10 degrees of malalignment in either knee will have been excluded.

Furthermore, the independent radiologist will have evaluated the screening X-rays to determine the following exclusion criteria for the index knee:

- Presence of osteochondromatosis
- History of ACL repair, reconstruction or injury
- History of cartilage repair surgery
- X-ray findings of acute fracture(s)
- Severe loss of bone density
- Avascular necrosis

- Severe bone or joint deformity in the index knee
- Advanced cases of gout
- Advanced cases of Paget
- Acromegaly
- Osteochondritis dissecans

The independent radiologist will have confirmed the eligibility of screened subjects based on the imaging enrollment criteria. In the event the independent radiologist determined that a subject is ineligible based on an imaging finding, the decision of the independent radiologist would have prevailed.

All the Screening X-rays were paid for by the Cingal 16-02 study and were free of charge to the subject. The images acquired for the Cingal 16-02 trial will have been transferred from the imaging site to the Central Imaging Core lab electronically and are available for use within Cingal 17-02. The X-rays will have been identified by the subject's study identification (ID) number. No personal identifiable information would have been included on the image.

10.2.8 Medical History

A complete medical history will have been obtained at the Screening Visit for Cingal 16-02 and will be utilized for Cingal 17-02. The medical history will have included an inquiry of past medical conditions in the following body systems: neurological, psychological, cardiovascular, hematological, respiratory, endocrine/metabolic, musculoskeletal, and immunologic (including allergies). The medical history will also include an assessment of the subject's history of the following:

- History/duration of knee OA
- History of operative arthroscopies
- History of open surgical procedures of either knee
- History of open surgical procedures of either hip
- History of IA injections including HA and steroid
- History of electromagnetic stimulation therapy
- History of other OA surgeries
- History of other OA procedures
- History of other OA abnormalities

10.2.9 Physical Evaluation of Knee

The Blinded Evaluator will perform the physical evaluation of the knee at the 39-week time point included in Section 10.1, Schedule of Events. This will include assessment of effusion grade of both knees (none, mild, moderate or marked), symptoms (e.g. persistent knee pain, limited morning stiffness and reduced function) and signs (crepitus, restricted movement and bony enlargement). Knee circumference in cm will also be measured in the index knee.

10.2.10 Range of Motion

The ROM will assess the maximum flexion and extension in degrees using a goniometer at the 39-week time point included in Section 10.1, Schedule of Events. The ROM will be documented as a hyphenated number. For instance, normal ROM in the knee is about 0-140 degrees.

10.2.11 WOMAC

The WOMAC index is self-administered and assesses the three dimensions of pain, disability and joint stiffness in knee and hip osteoarthritis using a battery of 24 questions (5 pain, 2 stiffness, 17 physical function) [14]. This trial will utilize the VAS version of the WOMAC index. The subject will be trained on how to complete the WOMAC which will be collected at the 39-week time points indicated in Section 10.1.

10.2.12 Medications

Medications that the subject may have been taking prior to enrollment in Cingal 16-02 for conditions unrelated to the treatment of knee osteoarthritis, other than analgesics including NSAIDs, may be continued through to Cingal 17-02 as long as they will not interfere with study assessments. If the subject was taking oral glucosamine and/or chondroitin sulfate products for the treatment of knee osteoarthritis prior to signing the informed consent form for Cingal 16-02, the products may be continued through to Cingal 17-02, but the subject must maintain a stable regimen for the duration of the Cingal 16-02 and the Cingal 17-02 studies.

10.2.12.1 Restricted Medications

All analgesics other than acetaminophen/paracetamol are prohibited during the study. This includes, but is not restricted to, NSAIDs, opioids and topical agents for treatment of OA in the index knee. Topical corticosteroids are allowed at any other site other than the index knee. The analgesic medication use will be monitored at each subject visit through review of the subject diary.

The use of IA injection of steroids in any joint and the use of IA injection of viscosupplements in the knee joint is prohibited throughout the study. The use of immunosuppressive agents such as

cyclosporine, methotrexate are prohibited throughout the study.

10.2.12.2 Rescue Medications

Acetaminophen/paracetamol (up to a maximum of 4.0 grams per day per the package insert or as per regional limitations) will be allowed as the rescue medication for the treatment of joint pain for the duration of Cingal 17-02. At least forty eight hours prior to the 39 week follow-up visit the subject should discontinue use of the rescue medication.

At the Screening Visit for Cingal 17-02, the rescue acetaminophen/paracetamol specifically labelled for use within Cingal 17-02 will be dispensed. The rescue medications provided to the subject for Cingal 16-02 should be returned to the investigational site at the Cingal 16-02 26 week follow up visit.

The subject should be instructed to bring the rescue medication with them to 39-week follow-up visit for a pill count. Additional rescue acetaminophen/paracetamol will be dispensed as needed only if there is an unscheduled the follow-up visit before the 39 week follow up visit.

10.2.12.3 Concomitant Medications

A medication is considered concomitant if taken after signing the ICF and up to and including the 39 week follow-up visit. Data on medications will include: medication name, dose, unit, route, frequency, start date, stop date, indication and whether the medication was taken for an AE.

At each study visit, the subject will be asked about any new medications that were started since the last visit. Indications for any new medications during the study period will be recorded as AEs, unless the medications are administered for a pre-existing condition.

10.2.13 Subject Diary

The subject diary will be dispensed at the Screening Visit and the subject will receive training on when and how to complete the diary. The subject diary will be used to collect information on medication usage including rescue medications, concomitant therapies (e.g. physical therapy) and AEs. The subject diary will be reviewed by site staff to determine if there are AEs that need to be captured within the Electronic Data Capture (EDC) system and to assess rescue medication usage and compliance with the protocol.

10.2.14 EuroQoL EQ-5D

Outcomes information from the subject-completed EuroQol EQ-5D will be obtained at the 39-week follow up specified in Section 10.1, Schedule of Events. The EQ-5D is a standardized measure of health status developed by the EuroQol Group which is applicable to a wide range of health conditions

and treatments. The EQ-5D provides a simple descriptive profile and a single index value for health status that can be used in the clinical and economic evaluation of health care as well as in population health surveys [15].

The EQ-5D is designed for self-completion by respondents and consists of 2 pages - the EQ-5D descriptive system and the EQ visual analog scale (EQ VAS). The EQ-5D descriptive system comprises the following 5 dimensions: mobility, self-care, usual activities, pain/discomfort and anxiety/depression [15]. The subject is asked to indicate his/her health state by ticking (or placing a cross) in the box against the most appropriate statement in each of the 5 dimensions. The EQ VAS records the subject's self-rated health on a vertical VAS where the endpoints are labeled 'Best health you can imagine' and 'Worst health you can imagine' as shown in Appendix 3. This information is used as a quantitative measure of health outcome as judged by the individual respondents [15].

10.2.15 Patient Global Assessment

The Patient Global Assessment (Appendix 2) is a VAS that will be completed by the subject at the 39 week follow up visit as specified in Section 10.1, Schedule of Events, to determine the Patient Global Assessment of response to therapy score. "Considering all the ways the osteoarthritis in your study index knee affects you, what is your assessment of how much your study knee is bothering you today?"

10.2.16 Evaluator Global Assessment

The Evaluator Global Assessment (Appendix 2) will be completed by the Blinded Evaluator at the 39 week follow up visit as specified in Section 10.1, Schedule of Events. To reduce the potential for bias, it is important for the Blinded Evaluator to complete the Evaluator Global Assessment prior to collecting the Patient Global Assessment.

The Blinded Evaluator will be asked "Considering all the ways the osteoarthritis in the patient's index knee affect him/her, what is your assessment of how much the patient's knee is bothering him/her today?"

10.2.17 Blinding

During the Cingal 16-02 trial the Treating Physician will have been aware of the differences between the Clinical Trial Materials and will have been unblinded, therefore; there were two clearly defined roles of a **Treating Physician** (unblinded) and a **Blinded Evaluator** (blinded) at each site. The site personnel fulfilling these roles will remain the same in Cingal 16-02 and Cingal 17-02.

- **Treating Physician:** The Treating Physician is most often the PI. He/she will have administered

the Cingal, Monovisc or Triamcinolone Hexacetonide (TH) injection but will not participated in the efficacy evaluations in either Cingal 16-02 or Cingal 17-02.

- **Blinded Evaluator:** The Blinded Evaluator will be a physician, research nurse, registered physiotherapist or physician assistant trained by the PI to perform the assessments outlined in the Cingal 16-02 and Cingal 17-02 protocols. The Blinded Evaluator will have completed the physical evaluation of both knees, ROM assessments of both knees, and the Evaluator Global Assessment for both Cingal 16-02 and Cingal 17-02 trials.

The identity of the syringes would not have been revealed during the Cingal 16-02 trial to the patients or the blinded evaluator. This blinding of the treatments given to the patients in the Cingal 16-02 trial will be maintained for the patients and the blinded evaluators in the Cingal 17-02 trial.

10.3 Screening

Each subject will indicate his or her willingness to participate in the study by signing the ICF. Subjects will maintain the unique subject ID (e.g., 01-001) allocated during the Cingal 16-02 trial where the first two digits represent the number assigned to the investigative site and the last three digits represent the subject number. The number will be recorded on the Enrollment Log and in the subject's electronic Case Report Forms (eCRFs). Subjects will be identified by the same unique subject ID for the duration of their participation in both the Cingal 16-02 and the Cingal 17-02 trials.

All data collected in the clinical trial Cingal 16-02 will be utilized in Cingal 17-02. The demographics and assessments conducted at screening and baseline for Cingal 16-02 will be utilized as the demographic and baseline data for Cingal 17-02.

The following screening and eligibility data will be collected at the Screening Visit for Cingal 17-02:

- Informed Consent
- Eligibility Data collected in Cingal 16-02 will be utilized for Cingal 17-02
- Distribute Subject Diary
- Assess AEs
- Assess Concomitant Medications
- Dispense Rescue Medication labelled for Cingal 17-02

During the Screening Visit inform the subject about discontinuation of all analgesics including NSAIDs except acetaminophen/paracetamol. Acetaminophen/paracetamol will be used as a rescue pain medication through the completion of the study, however; acetaminophen/paracetamol should be discontinued at least 48 hours before each follow-up study visit. Subjects who are taking oral

glucosamine and chondroitin sulfate products should be informed that a stable dose of these supplements must be maintained for the duration of the study.

10.4 Post-Treatment Follow-Up

All study subjects will have follow-up assessments at 39 weeks after injection day in Cingal 16-02 to evaluate effectiveness of the treatment and to assess AEs and protocol compliance. The Blinded Evaluator will evaluate the clinical status of the subject at each visit.

More than 48 hours prior to the visit, the subject will be reminded of the visit date and time, the need to abstain from acetaminophen/paracetamol for at least 48 hours prior to each follow-up visit and the requirement to bring their subject diary and the acetaminophen/paracetamol for a pill count with them to the appointment.

If the subject arrives for a study visit without discontinuing acetaminophen/paracetamol for at least 48 hours prior to the visit, the visit should be rescheduled within the allowed window of time. Study assessments should be performed as soon as possible and the protocol deviation, if applicable, recorded in the source and eCRF. The subject must be re-educated about the importance of protocol compliance.

If the subject does not come in at the expected time, at least three attempts will be made to contact the subject in order to accomplish maximum subject compliance with the follow-up schedule.

The following post-treatment visits will be performed. The subject will be asked whether any concomitant medications have been taken. All assessments will be done by the Blinded Evaluator.

39 Weeks \pm 7 Days

- Confirm Rescue Medication Washout
- Evaluate Subject Diary
- Count Rescue Medication Pills (if needed)
- Physical Evaluation (both knees)
- ROM (both knees)
- WOMAC (both knees)
- Patient Global Assessment
- Evaluator Global Assessment
- EuroQol
- Assess Concomitant Medications

- Assess AEs

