2 DEFINITIONS

Baseline: The assessments performed prior to the study injection after the Screening Visit.

Blinded Evaluator: The Blinded Evaluator will be a physician, research nurse, registered physiotherapist or physician assistant trained by the PI to perform the assessments outlined in the protocol. The Blinded Evaluator will complete the physical evaluation of both knees, range of motion (ROM) assessment of both knees, and the Evaluator Global Assessment.

End of Study: End of study is defined as the last subject's last visit.

Enrolled: A subject who has signed the informed consent form (ICF) is enrolled.

Index Knee: The knee that meets the eligibility criteria for treatment. The index knee may also be termed the "study knee". In subjects with bilateral knee Osteoarthritis (OA), where both knees meet eligibility criteria, the more symptomatic knee is the index knee.

Ethics Committee (EC): EC refers to an independent body (e.g. Research Ethics Boards, Independent Ethics Committees) whose responsibility is to ensure the protection of rights, safety and well-being of human subjects involved in a trial. Committees with these responsibilities will be referred to in this document as Ethics Committees.

Rescue Medication: Acetaminophen/paracetamol will be distributed as the rescue medication. It is the only medication that should be taken for knee pain during the entire study. Rescue medication will be discontinued at least 48 hours prior to Baseline and all follow-up visits.

Treating Physician: The Treating Physician will most often be the Principal Investigator (PI). He/she will administer the Cingal®, Monovisc® or steroid injection but will not participate in the efficacy evaluation.

Treatment Failure: A subject who undergoes a procedure or uses a medication (other than the rescue medication) for the treatment of OA in the index knee at any time after the study injection through the 39 week visit.

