7.3 Exploratory Endpoints

Any comparisons between groups (Cingal, Monovisc, TH), within groups and / or time points (from baseline through to 39 weeks) not described in the primary or secondary endpoints may be presented in the exploratory endpoints including:

[figure not shown]
- EuroQol (EQ-5D)
- WOMAC Pain Score (100mm VAS)
- OMERACT-OARSI
- Total WOMAC
- WOMAC Stiffness Score
- WOMAC Physical Function
- Patient Global Assessment
- Evaluator Global Assessment
- Range of Motion
- Rescue Medication Usage
- Number of Treatment Failures due to Additional Procedure or Use of Disallowed Medication

7.4 Safety Endpoint:

The incidence, timing, severity, and relationship to treatment of all Adverse Events (AE) will be collected and coded using Medical Dictionary for Regulatory Activities (MedDRA). Local injection site and non-local events will be recorded separately.

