10 STUDY PROCEDURES

10.1 Schedule of Events

	Pre-Treatment	Treatment		Post-Treatment Follow-Up Visits						17-02 Follow-Up Visits	
		Day 0 (7-14 days after screening visit)		1 week	3 weeks	6 weeks	12 weeks	18 weeks	26 weeks	Consent	39 Weeks
Assessments	-7 to -14 Days	Day 0 (7-14 days after screening visit)		1 week	3 weeks	6 weeks	12 weeks	18 weeks	26 weeks	Consent	39 Weeks
	Screening	Baseline	Treatment	±3 days			± 1 week				
Informed Consent	X									X	
Demographics Medical History	X										
Physical Exam, Vitals, BMI	X										
Urine / Blood Pregnancy Test	X										
Chemistry/Hematology/Urinalysis	X										
Bilateral Knee X-rays and assessment of K-L	X										
Review of X-rays by Independent Radiologist	X										
Physical Evaluation (Both Knees)	X	X		X	X	X	X	X	X		X
ROM (Index Knee)	X	X		X	X	X	X	X	X		X
ROM (Contralateral Knee)	X	X					X		X		X
WOMAC (Both Knees)	X	X		X	X	X	X	X	X		X
Evaluation of Enrollment Criteria	X	X	X							X	
Stop Analgesics/NSAIDs except Paracetamol	X										
Assess D/C Paracetamol ≥ 48 hours before Visit		X		X	X	X	X	X	X	X	X
Paracetamol Dispense/Pill Count	X	X		X	X	X	X	X	X	X	X
Distribute Subject Diary	X										X
Randomization			X								
Aspiration/ Evaluation of Synovial Fluid			X								
IA Injection			X								
Evaluate Diary		X		X	X	X	X	X	X		X
EuroQol		X		X	X	X	X	X	X		X
Patient Global Assessment		X		X	X	X	X	X	X		X
Evaluator Global Assessment		X		X	X	X	X	X	X		X
Concomitant Medication Assessment				Throughout the study							
Adverse Event Assessment				Throughout the study							

† -Cells in grey indicate assessments conducted only during Cingal 16-02 trial.

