12.1.3 Exploratory Endpoints

Any comparisons between groups (Cingal, Monovisc, TH), within groups and / or time points (from baseline through to 39 weeks) not described in the primary or secondary endpoints may be presented

in the exploratory endpoints including:

- EuroQoL (EQ-5D)
- WOMAC Pain Score (100mm VAS)
- OMERACT-OARSI
- Total WOMAC
- WOMAC Stiffness Score
- WOMAC Physical Function Score
- Patient Global Assessment
- Evaluator Global Assessment
- Range of Motion
- Rescue Medication Usage: Difference in analgesic use measured by number of pills taken between visits will be compared between treatment groups descriptively.
- Number of Subjects Considered Treatment Failures: Treatment Failure: A subject who undergoes a procedure or uses a medication (other than the rescue medication) for the treatment of OA in the index knee at any time after the study injection through the 39 week visit.

For the exploratory analyses, the continuous variables will be analyzed via an analysis of variance and contrasts used to assess the prescribed comparisons. For the discrete variables, a Fisher's exact test will be used to assess the desired comparisons.

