4.1.4 Exploratory Endpoints

Any comparisons between groups (Cingal, Monovisc, TH), within groups and / or time points (from baseline through to 39 weeks) not described in the primary or secondary endpoints may be presented in the exploratory endpoints including:

- EuroQoL (EQ-5D)
- WOMAC Pain Score (100mm VAS)
- OMERACT-OARSI
- Total WOMAC
- WOMAC Stiffness Score
- WOMAC Physical Function Score
- Patient Global Assessment
- Evaluator Global Assessment
- Range of Motion
- Rescue Medication Usage: Difference in analgesic use measured by number of pills taken between visits will be compared between treatment groups descriptively.
- Number of Subjects Considered Treatment Failures: Treatment Failure: A subject who undergoes a procedure or uses a medication (other than the rescue medication) for the treatment of OA in the index knee at any time after the study injection through the 12 week visit.

For the exploratory analyses, the continuous variables will be analyzed via an analysis of variance and contrasts used to assess the prescribed comparisons. For the discrete variables, a Fisher's exact test will be used to assess the desired comparisons.

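### SAP 4.1.4 ends the treatment-failure count at week 12 where the protocol runs to week 39; separately, the week-39 washout and reschedule step covers paracetamol only

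*Protocol*

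**What the plan says.** **Treatment failure.** Protocol section 2 classes as a failure anyone given an additional procedure for the condition, and equally anyone who "uses a medication (other than the rescue medication) for the treatment of OA in the index knee at any time after the study injection", with week 39 as the end of the period. Protocol 12.1.3 repeats it: "for the treatment of OA in the index knee at any time after the study injection through the 39 week visit". SAP 4.1.4 has the same sentence with a different end point: "for the treatment of OA in the index knee at any time after the study injection through the 12 week visit". Protocol 7.3 and SAP 3.3 both list the endpoint as "Number of Treatment Failures due to Additional Procedure or Use of Disallowed Medication", within exploratory comparisons that may run from baseline to week 39.

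**Washout before the week-39 visit.** Protocol 10.4 has a reminder, a washout check and a reschedule trigger, all tied to paracetamol: "If the subject arrives for a study visit without discontinuing acetaminophen/paracetamol for at least 48 hours prior to the visit, the visit should be rescheduled". The sentence goes on to limit rescheduling to the allowed window. The text that follows has the assessments done as soon as possible and any deviation recorded. The row in the Schedule of Events (10.1) reads "Assess D/C Paracetamol ≥ 48 hours before Visit".

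**Other analgesics.** Protocol 10.2.12.1 bans them for the whole study and has their use monitored by diary review. At the 17-02 Screening Visit (10.3) the site must "inform the subject about discontinuation of all analgesics including NSAIDs except acetaminophen/paracetamol". The concomitant-medication record (10.2.12.3) holds "medication name, dose, unit, route, frequency, start date, stop date, indication and whether the medication was taken for an AE". Section 16.9 makes prohibited medication a deviation, keeps the subject under efficacy follow-up, and gives unauthorised treatment as an example of a major violation.

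**Analysis.** Protocol 12.1.1 and 12.5 and SAP 4.1.2 and 4.5 test the OMERACT-OARSI responder rate in the ITT population by Fisher's exact test, with imputation of missing values. A secondary Per Protocol analysis excludes major violators.

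**The concern.** The two documents define one endpoint over different periods. The SAP is what the programmer will follow, so the reported number of failures per arm would stop at week 12. Use of disallowed medication between then and week 39 would not appear in it, although that is the stretch that bears on a week-39 endpoint.

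The washout text raises a different question. The one permitted analgesic postpones scoring if taken within 48 hours, while a banned one does not. WOMAC asks about the last 48 hours (Appendix 1), so an NSAID or opioid taken then could lower the score for reasons unrelated to the injection. No rule in either document keeps such a score from counting as a response in the ITT analysis. The failure count is the pre-specified place to see whether disallowed use differs by arm, and under the SAP wording it does not reach this period.

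**Working it through.** **1. Length of the gap in the SAP definition.** Inputs: 39 weeks (Protocol section 2 and 12.1.3) and 12 weeks (SAP 4.1.4), both nominal. Uncovered: 39 − 12 = 27 weeks; 27/39 = 69%.

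**2. Is week 12 a deliberate choice?** SAP 3.3 and the opening sentence of SAP 4.1.4 itself set the exploratory scope at baseline to 39 weeks. SAP 4.1 says that the SAP details the analysis described in the protocol. Nothing explains a 12-week limit, so it conflicts with the protocol and with the SAP's own scope.

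**3. What happens after use of each drug before week 39.**

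| Step | Paracetamol | Other analgesic |
|---|---|---|
| Status | Permitted, 48-hour stop | Banned throughout |
| Instruction at 17-02 Screening | Stop 48 hours before visit | Stop altogether |
| Pre-visit reminder (10.4) | Yes | No |
| Washout check (10.1, 10.4) | Yes | No |
| Reschedule within window (10.4) | Yes | No |
| Diary and medication review | Yes | Yes |
| Recorded as deviation | If applicable | Yes |
| ITT score | As observed | As observed |
| Per Protocol set | No specific rule | May be removed as major violator |

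**4. Sensitivity of the primary test.** The plan gives no responder rates and no rate of prohibited use, so there is no figure of its own to reproduce. Planned sizes are 256 Cingal and 64 TH (Protocol 12.1). One reclassified responder moves the Cingal rate by 1/256 = 0.39 points and the TH rate by 1/64 = 1.56 points.

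Assumed: TH 32/64; three possible Cingal results; 2% (5 of 256, 1 of 64) or 5% (13 of 256, 3 of 64) of an arm moved from responder to non-responder. Every user is taken to be a responder, so these are outer bounds for that level of use. Two-sided Fisher p-values:

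| Cingal vs TH (difference) | As observed | 2% Cingal | 2% TH | 2% both | 5% Cingal | 5% TH | 5% both |
|---|---|---|---|---|---|---|---|
| 150/256 vs 32/64 (8.6 points) | 0.259 | 0.399 | 0.160 | 0.263 | 0.675 | 0.067 | 0.265 |
| 164/256 vs 32/64 (14.1 points) | 0.0449 | 0.088 | 0.031 | 0.064 | 0.206 | 0.0069 | 0.0665 |
| 180/256 vs 32/64 (20.3 points) | 0.0030 | 0.0082 | 0.0018 | 0.0036 | 0.0305 | 0.0004 | 0.0041 |

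Only the middle row crosses 0.05, and it starts at 0.0449.

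**5. Direction.** Let p be the true responder rate and u the share of true non-responders who score as responders on a prohibited drug. The observed rate is p + (1 − p)u. With assumed true rates of 70% and 50% (20 points, Fisher power 82%):

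- u = 20% in both arms: 0.76 − 0.60 = 16 points, power 69%.
- u = 5% Cingal, 20% TH: 0.715 − 0.60 = 11.5 points, power 40%.
- u = 20% Cingal, 5% TH: 0.76 − 0.525 = 23.5 points, power 94%.

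Equal use shrinks a true difference by the factor (1 − u). Unequal use can favour either arm.

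**The case against.** The paracetamol-only washout has a rationale. A permitted drug needs a timed stop, whereas a banned drug should not be in use at all, and the ban is repeated at 17-02 Screening and monitored through the diary. A visit can also be scored on paracetamol once the window closes, so the contrast is one of degree. Scoring deviators as observed is a legitimate ITT choice, and the Per Protocol analysis offers a check. All of this stands. It leaves a partial gap: detection leads to no postponement, and the Per Protocol set drops such subjects, where it drops them at all, without counting them as failures.

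On the SAP wording, the defence is that it affects only an exploratory count. That is right about its weight, but the count would still be wrong as written.

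A reader might go further and infer that prohibited analgesics go unmonitored, that the primary comparison is biased towards Cingal, or that the 12-week wording distorts the primary analysis. The documents support none of these. Use is monitored and recorded, no rate or imbalance of use is given, and treatment failure plays no part in the primary test.

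**Conclusion.** The SAP definition is wrong as written. It leaves 27 of 39 weeks (69%) out of the treatment-failure count and should be corrected whatever is decided on the rest. The effect is confined to an exploratory endpoint.

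The washout gap is real but modest, and closing it is an improvement to consider. Its effect on the ITT responder comparison cannot be sized or signed from the documents. The scenarios rest on assumed responder counts, assumed use, and the planned 256 and 64; joining 17-02 is optional, so actual numbers may be lower. They show only that a result close to 0.05 could depend on a few subjects. They are not evidence of bias.

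**What to change.** 1. **SAP 4.1.4:** change the end of the treatment-failure period from the 12 week to the 39 week visit. Cost: one correction.

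2. **Protocol 10.4 and the Schedule of Events:** extend the existing reminder, washout check and reschedule-within-window step to any non-permitted analgesic, exempting the stable low-dose cardioprotective aspirin allowed by criterion 14 in Protocol 9.1.3. If the window closes, score the visit and record the deviation, as is done for paracetamol. Cost: reworded items, and a few visits moved within the 7-day window. A 48-hour check does not reproduce the seven-day stop required before the injection, but it matches the WOMAC recall period.

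3. **Optional:** leave the ITT primary analysis as it is and pre-specify one supportive ITT analysis that counts treatment failures through week 39 as non-responders, and also identifies subjects scored within 48 hours of a non-permitted analgesic. Two details matter. Section 2 exempts only rescue medication, so stable glucosamine or chondroitin permitted by Protocol 10.2.12 must be excluded expressly, or compliant users would be failed. Start and stop dates alone cannot place an as-needed tablet within 48 hours of the visit, so the subject diary (10.2.13) must be used with the concomitant-medication record. Show the two components separately by arm. Cost: one table and the diary review behind it.
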